1.2.4 Conclusion

This study will aim to determine the feasibility of detecting tumor specific DNA mutations and DNA methylation abnormalities in biological fluids of patients with a variety of GI malignancies compared to tumor biopsies or resected tumor tissue. Additionally, we will compare the ability to detect these nucleic acids in serum, urine, and stool. A secondary endpoint will be to determine if detection of tumor specific nucleic acids can be used as markers of active disease. In addition, the study will aim to evaluate known markers of inflammation and fibrosis as possible markers of gastrointestinal toxicity in the serum, urine, and stool of patients receiving radiotherapy for gastrointestinal malignancies.

2.0 Eligibility Assessment and Enrollment

2.1 ELIGIBILITY CRITERIA

2.1.1 *Inclusion Criteria*

- 2.1.1.1 Age \geq 18 years
- 2.1.1.2 Histologically confirmed carcinoma of the gastrointestinal tract (esophagus, stomach, pancreas, bile duct, rectum)
- 2.1.1.3 Treatment plan includes radiotherapy to the site of the gastrointestinal malignancy on an NCI protocol
- 2.1.1.4 Paraffin embedded tumor tissue from biopsy adequate in amount to perform PCR and methylation specific PCR or willingness to undergo rebiopsy

2.1.2 *Exclusion Criteria*

- 2.1.2.1 Inability to provide informed consent
- 2.1.2.2 Patients who have a history of prior therapeutic radiation
- 2.1.2.3 Patients with evidence of distant metastases on initial staging evaluation
- 2.1.2.4 Patients with other cancers excluding non-melanomatous skin cancers or carcinoma in situ
- 2.1.2.5 Patients who have undergone complete resection of the gastrointestinal malignancy prior to protocol enrollment
- 2.1.2.6 History of inflammatory bowel disease
- 2.1.2.7 History of collagen vascular disease or disease of altered collagen metabolism (end stage renal disease or hepatic fibrosis due to chronic hepatitis)
- 2.1.2.8 History of hypersensitivity to radiation or a history of a disease which results in mucosal or other hypersensitivity to radiation (Ataxiatelangiectasia, Bloom's Syndrome, Human Immunodeficiency Virus, Fanconi anemia, nevoid basal cell carcinoma syndrome, Li-Fraumeni syndrome, and Nijmegen breakage syndrome)
- 2.1.2.9 Inability to return for followup visits
- 2.1.2.10 Patients who have previously received or are currently receiving MDX-101 (ipilimumab).
- 2.1.2.11 Diagnosis of HIV, Hepatitis B, or Hepatitis C

2.2 PRE-TREATMENT RESEARCH ELIGIBILITY EVALUATION

2.2.1 *Clinical Evaluations*

- History and Physical Examination within one month of entry: Specific items to document include:
 - Age
 - Primary tumor site
 - Primary tumor histology
 - Tumor stage
 - Baseline gastrointestinal function including RTOG acute toxicity scoring
 - Prior abdominal surgeries

- History of diseases known to affect systemic inflammatory states (ie. hypertension, liver function abnormalities, renal function abnormalities, cardiac disease, autoimmune disorders, collagen vascular disorders, and arthritis)

2.2.2 .Pathologic confirmation

Pathology report confirming carcinoma of the esophagus, rectum, or pancreas (outside report acceptable for study entry; pathology review by NIH to be performed if radiation therapy to be administered at NCI ROB).

2.3 PATIENT REGISTRATION

Authorized staff must register with the Central Registration Office an eligible candidate within 24 hours of signing the consent. A registration checklist from the Web site (http://camp.nci.nih.gov/dcs/rob/rob_index.html) must be completed and faxed to [contact].

3.0 STUDY IMPLEMENTATION

3.1 STUDY DESIGN

3.1.1 Overall Trial Design (see Appendix IA)

Patients planned to receive radiotherapy for carcinoma of the esophagus, stomach, pancreas, rectum, or other biliary malignancies as part of their primary therapy will be potential candidates for enrollment on this protocol. This is not a study of an experimental therapy and will be administered in conjunction with protocol therapy for patients receiving radiation as part of the treatment of a gastrointestinal carcinoma. 120 patients will be included from the following sites: 30 patients with esophageal or GE junction cancer, 30 patients with locally advanced biliary malignancies (including pancreas and bile ducts only), 30 patients with resected biliary malignancies (including pancreas and bile ducts only), and 30 patients with rectal cancer.

Serum, plasma, urine, and stool samples will be collected prior to any therapy (surgery excluding biopsy, systemic therapy, or radiotherapy), prior to radiotherapy (if different from "prior to any therapy"), at completion of radiation (within the final five fractions), and at 1, 3, 6, 12, 24, and 36 months follow-up

The Intestinal Permeability Assessment will be performed following protocol sample collection (above) at the following time points: prior to any therapy, prior to radiotherapy (if different than "prior to therapy"), at 1 month follow-up, and at 3 months follow- up.

Tumor tissue obtained at biopsy or resection will be screened for a defined panel of mutations using PCR and abnormal methylation status will be determined by methylation specific PCR. Serum, urine, and stool samples obtained prior to therapeutic intervention will be screened for the same panel of markers. Serum, urine, and stool obtained during treatment and at follow-up will be evaluated for these

same DNA markers and correlated to evidence of gross residual disease on physical examination and follow-up imaging.

Potential serum, plasma, and stool markers of gastrointestinal toxicity will be correlated to validated measures of gastrointestinal toxicity.

3.2 PROTOCOL THERAPY ADMINISTRATION

3.2.1 Specimen Collection

3.2.1.1 Tumor tissue

3.2.1.1.1 Collection guidelines

- Biopsy material will be snap frozen in liquid nitrogen and transported to the laboratory of [name] for storage at -80C.
- An NIH pathologist will be involved in selecting tumor tissue for experimental use if obtained at the time of resection to ensure adequate tissue is reserved for pathologic diagnosis and determination of margin status. Tumor tissue from resection will only be obtained if surgical therapy is the first form of therapy for the malignancy (i.e., no radiation or chemotherapy is delivered prior to resection). This tissue will be snap frozen in liquid nitrogen and transported to the laboratory of [name] for storage at -80C.

[name]
[name]
[name]
[contact]

- Patients in whom a biopsy would be considered more than minimal risk (i.e., pancreatic tumor biopsy not obtained at the time of surgery or already planned invasive procedure) are exempt from the biopsy requirement; however attempts will be made to obtain prior biopsy specimens from NIH or outside facilities if available.

3.2.1.1.2 Collection Schedule

Tumor tissue is obtained at biopsy or resection (pre-treatment only) at baseline

3.2.1.1.3 Specimen analysis

Tumor tissue will be screened for a panel of mutations with PCR and abnormal methylation with methylation specific PCR (see appendix IIA&B)

3.2.1.2 Blood, Urine, and Stool Specimens

3.2.1.2.1 Collection guidelines (see Appendix IA)

Nurses at the radiation oncology clinic will collect blood, urine, and stool samples before, during and following therapy.

- Blood –

- 10 cc in one EDTA tube for plasma; place only EDTA containing tube immediately on ice, EDTA containing tube must be collected first,

- o 24cc total in serum separator tube (SST) for serum,
- Stool – at least 10 gm in a sterile collection cup.
- Urine – at least 15 cc in a sterile collection cup

3.2.1.2.2 Collection Schedule

Pre- treatment, pre-radiotherapy (if different than pre-treatment) at completion of radiotherapy and in follow- up at 1, 3, 6, 12, 24, and 36 months

3.2.1.2.3 Specimen Analysis (see Appendix IB)

- All samples will be sent to the laboratory of [name]. for appropriate processing and storage
- Plasma samples will be processed and snap frozen at -80° C until the time of use for TGF β 1 assays.
- Serum, urine, and stool will be processed, aliquoted, snap frozen, and stored at -20° C (stool) or -80° C (urine, serum, and plasma) until use

3.2.1.3 Handling of Specimens collected for Research Purposes

- Tissue, serum, plasma, urine, and stool samples collected in the course of this research project may be banked and used in the future to investigate new scientific questions related to this study. However, this research may only be done if the risks of the new questions were covered in the consent document.
- No germline mutation testing will be performed on any of the samples collected.
- At the completion of the protocol, the investigatory will dispose of all specimens in accordance with the environmental protection laws, regulations and guidelines of the Federal Government and the State of Maryland.
- Any loss or unintentional destruction of the samples will be reported to the IRB.
- Any new use of the samples will require prospective IRB review and approval.

3.2.2 *Intestinal permeability test*

The Intestinal Permeability Assessment directly measures the ability of two non-metabolized sugar molecules, mannitol and lactulose, to permeate the intestinal mucosa. Mannitol is easily absorbed and serves as a marker of transcellular uptake, while lactulose is only slightly absorbed and serves as a marker for mucosal integrity. Intestinal permeability tests are commercially available. (see collection schedule in 3.3)

3.2.2.1 Collection guidelines (see Appendix IA):

- These assessments will be performed following protocol sample collection before, during and following therapy.
- The patient will fast over night for 8 hours and will then drink a "challenge" drink supplied by Genova Diagnostics composed of 5gm of lactulose and 1gm of mannitol. Patients are asked to avoid non-steroidal anti-inflammatory drugs for twenty-four hours prior to the test, unless medically required (ie low dose aspirin for cardiac disease).

- Urine is collected over six hours and refrigerated until the patient returns to the ROB clinic.

3.2.2.2 Collection Schedule

Pre-treatment and in follow-up at 1 and 3 months.

3.2.2.3 Specimen analysis

- The urine will be collected in a collapsible jug provided by Genova Diagnostics which will be stored in the clinic prior to use and provided to the patient prior to the ingestion of the challenge drink.
- The 6 hour urine will be brought to the ROB clinic by the patient.
- The specimen will then be transported to the laboratory of [name] for shipment to Genova Diagnostics.
 - All personal identifiable information will be removed and the specimen will be labeled by a code based on the patient's enrollment number on the protocol
 - The urine will be shipped to Genova Diagnostics for further testing. The jug is specially designed to serve as packaging as well and has a prepaid and preaddressed shipping label via DHL shipping. The address on this shipping label will be:

Genova Diagnostics
[name]
[name]

3.2.3 Toxicity Assessment

3.2.4.1 Collection Guidelines

Radiation induced gastrointestinal toxicity will be measured with the RTOG toxicity scoring schemas (Appendices IIIA and IIIB)

3.2.4.2 Collection Schedule

Pre-treatment, at completion of treatment and in follow-up at 1, 3, 6, 12, 24, and 36 months

3.3 ON STUDY EVALUATION

3.3.1 Pre-Treatment (baseline)

- Informed consent obtained
- Clinical evaluation

See 2.2.1

Baseline acute RTOG toxicity assessment (appendix IIIA)

- Laboratory Evaluation

See 2.2.2

Hepatitis B

Hepatitis C

CBC, ALT, AST, total bilirubin, serum BUN, serum creatinine

- Research Specimen Collection:

- Blood, urine, stool (see 3.2.1.2)
 - baseline intestinal permeability test, 6 hour urine (see 3.2.2)

- Pathologic confirmation and biopsy of tumor tissue (see 2.2.3)

3.3.2 *Radiation Treatment Phase*

- Patients will receive radiotherapy for carcinoma of the esophagus, stomach, pancreas, bile ducts, or rectum on an NCI protocol
- At completion of radiation (within the final five fractions)
 - Research Specimen Collection:
 - Blood, urine, stool (see 3.2.1.2)
 - Toxicity Evaluation: RTOG - Acute Radiation Morbidity Scoring Criteria (Appendix IIIA)

3.3.3 *Post Active Treatment Evaluation (follow- up)*

- 3.3.3.1 Patients will be seen for routine follow-up at 1, 3, 6 and 12, 24, and 36 months post-radiotherapy.

- 3.3.3.2 These follow- up visits will include:

- Clinical Evaluation
 - A complete history and physical exam detailing the patient's disease status, bowel function, and medication requirements related to gastrointestinal toxicity. All post-radiotherapy adjuvant therapy will be recorded.
 - Toxicity Evaluation: Complete RTOG - Radiation Morbidity Scoring Criteria (Appendix IIIA, acute at 1 month and IIIB, late at 3, 6, and 12, 24, and 36 months follow-up.
- Laboratory Evaluation
 - As clinically indicated. The presence of accepted serum tumor markers (ie CA 19-9) in excess of defined maximum ranges will be recorded as evidence of disease recurrence.
 - CBC, ALT, AST, total bilirubin, serum BUN, serum creatinine
- Research Specimen Collection:
 - Blood, urine, stool (see 3.2.1)
 - intestinal permeability test, 6 hour urine (see 3.2.2) AT ONE AND THREE MONTHS ONLY
- Radiologic Evaluation
 - As clinically indicated by primary site and primary protocol. For the purpose of radiographically evaluating disease status to correlate to laboratory findings the following radiographic evaluations may be included for determination of disease recurrence: CT, plain films, bone scans, MRI, US, and PET.
- Response Category Evaluation (as in 5.2)

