5.2 Response Criteria

This is not a treatment study and will be administered in conjunction with protocol therapy for patients receiving radiation as part of treatment of their gastrointestinal carcinoma. Response will be assessed according to the patient's primary treatment protocol, as clinically indicated based on their disease site. For consistency in addressing this protocol's objectives, we will use this response information to group patients into the following categories at their follow- up time points (1,3,6,12, 24 & 36 months):

5.2.1 Complete response (CR) is defined as no clinical, radiographic or laboratory evidence of disease following treatment

5.2.2 All other classifications of the RECIST criteria (partial responders, stable disease, and progressive disease) will be considered not a CR.(as defined in 5.2.1). These patients will be considered not complete responders for the purposes of comparison to serum markers.

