For the first primary objective, tumor-specific DNA mutation markers will be collected at baseline (before any therapy and before radiation begins) at completion of radiation therapy and at 1, 3, 6, 12, 24, and 36 months of follow-up. Of interest is examining whether changes in the average mutation frequency (of the disease-specific mutations given in Appendix IIA) effects response to therapy, overall survival, and disease-free survival among complete responders to all therapy. Various analyses will be done to address with objective. These analyses will be done separately by tumor type as well as combined over tumor type (assuming that the relationship between marker changes and disease outcome do not vary across tumor type). First, we will examine the relationship between changes in mutational status over time and survival with Cox proportional hazards models. The relationship between changes in mutational status over time and complete response will be estimated using logistic regression analysis. One key primary analysis will be to examine whether having all tumor-specific markers being negative at 3 months after radiation therapy ends is associated with long-term survival. Note that based on the tumor marker prevalences in the literature (see Appendix IIC) and an assumption that marker prevalence is independent across the various markers, the probability of having at least one mutation which is positive before treatment is very high. Our sample size calculations assume that 50% of patients will have all tumor-specific markers negative 3 months after radiation therapy ends. Based on conducting a two-sided log-rank test at the 0.05 significance level with a total enrollment of 120 patients, we would have 89% power to detect a difference between 35% overall 2-year survival in the positive marker group and 65% overall 2-year survival in the negative marker group. We will have power only to detect large differences for the tumor-specific analyses. With 30 patients in each group (15 patients in the positive and negative groups, respectively), we would have 83% power to detect a difference in 2 year survival of between 80% in the marker negative group and 20% in the marker positive group using a log-rank test at the 0.05 significance level. The above sample size calculation depends heavily on the assumption that 50% of patients will have all tumor-specific markers negative at 3 months. The power may be severely diminished if this proportion deviates too much from 50%. Thus, alternative similar analyses will also be conducted. For example, we will compare survival by whether the change in tumor-specific marker frequency from

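### Does recording an above-range serum marker as evidence of recurrence, with no confirmation rule, undermine the response and disease-free survival analyses?

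*Combined protocol and SAP*

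**What the plan says.** Section 3.3.3, under laboratory evaluation at follow-up, gives the rule: "The presence of accepted serum tumor markers (ie CA 19-9) in excess of defined maximum ranges will be recorded as evidence of disease recurrence". Laboratory and radiologic evaluations there are both done as clinically indicated. The same visit list sends the response category to Section 5.2.

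Section 5.2 takes response from the patient's "primary treatment protocol, as clinically indicated based on their disease site". It then says that "we will use this response information to group patients into the following categories" at 1, 3, 6, 12, 24 and 36 months. CR means "no clinical, radiographic or laboratory evidence of disease following treatment"; everything else is not a CR.

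Section 3.1.1, the design overview, says the follow-up samples will be evaluated for the "same DNA markers and correlated to evidence of gross residual disease on physical examination and follow-up imaging".

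Section 5.4.1 names the outcomes of interest as "response to therapy, overall survival, and disease-free survival among complete responders to all therapy". For response it states: "The relationship between changes in mutational status over time and complete response will be estimated using logistic regression analysis". It gives no definition of a DFS event or its date.

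**The concern.** Taken together, Sections 3.3.3 and 5.2.1 let one unconfirmed laboratory value decide that a patient is not in CR. Section 1.2.1 says that none of these serum markers is fully tumour-specific and that inflammation and benign disease can raise them. The exclusion criteria remove some such conditions (inflammatory bowel disease, hepatitis B and C), but not every source of a benign rise.

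The DNA markers would then be judged against a status partly set by a marker the protocol calls non-specific. A benign rise could score a true complete responder as a non-responder, dilute the association between DNA markers and CR, and perhaps keep that patient out of the DFS set. With no DFS event rule, two analysts could count different events from the same data. Section 3.1.1 also seems to use another reference standard, since it names only examination and imaging. CR, recurrence and DFS all serve the first primary objective, so the point deserves a check.

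**Working it through.** **1. The plan's own power figure.** Inputs from Section 5.4.1: 120 patients, half marker-negative at 3 months, 2-year overall survival 35% against 65%, two-sided 0.05.

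- Hazard ratio (exponential): ln(0.35)/ln(0.65) = 2.437.
- Deaths by 2 years: 60 × 0.65 + 60 × 0.35 = 60.
- Freedman log-rank power: Φ(√60 × (2.437 − 1)/(2.437 + 1) − 1.96) = 89.9%, against the stated 89%.

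The endpoint is death, so no rule about serum markers enters this calculation.

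**2. Can a marker alone exclude CR?** Yes, by inference: 3.3.3 makes the raised value evidence of recurrence, and 5.2.1 requires no laboratory evidence. No single sentence says so. The category is assigned through the primary treatment protocol, which is not among the documents and may have its own confirmation rule.

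**3. Does 3.1.1 conflict?** Not really. It is an overview sentence about gross residual disease, which examination and imaging naturally assess. Sections 3.3.3 and 5.2 concern recurrence and CR, a broader idea, and they agree with each other.

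**4. Size of the effect on CR.** The documents give no benign-elevation rate, testing share or CR rate, so this is an illustration at one visit. Assume:

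- a share t of true complete responders is tested (0.5 or 1);
- a fraction f of those tested has a benign elevation (0.02, 0.05 or 0.10), unrelated to DNA-marker status;
- true CR is 65% against 35% in groups of 60, borrowing the survival figures for scale.

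With r = t × f, observed CR is 0.65(1 − r) against 0.35(1 − r). Power is for a two-sided 0.05 comparison of two proportions, normal approximation, pooled variance under the null.

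| r | CR difference (points) | Odds ratio | Power |
|---|---|---|---|
| 0 | 30.0 | 3.45 | 91.8% |
| 0.01 | 29.7 | 3.40 | 91.2% |
| 0.025 | 29.25 | 3.34 | 90.4% |
| 0.05 | 28.5 | 3.24 | 88.8% |
| 0.10 | 27.0 | 3.07 | 85.4% |

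At r = 0.10, for example, the proportions are 0.585 and 0.315 and the odds ratio is (0.585/0.415)/(0.315/0.685) = 3.07.

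**5. DFS.** Section 5.2 regroups patients at six visits, and Section 5.4.1 does not say which visit fixes who is a complete responder to all therapy. A passing benign rise makes a patient non-CR at that visit. Whether it removes the patient from the DFS set cannot be derived, so no count of lost patients is justified.

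**The case for a change.** The best case for a change is that it costs almost nothing: one sentence defining the DFS event, a dated variable for marker-only elevations, and a second run of the same analyses. Settling the rule beforehand also prevents a choice made after seeing the data. The one-visit illustration may be too kind. With independent false-positive rates of 1%, 2%, 5% or 10% per visit and testing at all six visits, the chance of at least one false record is 1 − (1 − q)⁶ = 5.9%, 11.4%, 26.5% or 46.9%.

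Part of this stands. The DFS event and its date are indeed undefined, and that gap is wider than serum markers. The six-visit figures are correct arithmetic, but they assume testing at every visit, whereas 3.3.3 tests as clinically indicated, and independence between visits, which is doubtful for a benign condition that persists. They count any false record, not a wrong final status.

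The with-and-without analysis is a reasonable extra, but it does not say which definition should lead. Dropping marker-only findings has its own cost: some true recurrences would be dated later, in patients whose post-radiation scans Section 1.2.1 describes as hard to interpret. Section 3.3.3 does list imaging as a way to relate disease status to laboratory results. That wording is permissive, though, and may refer to the DNA markers, so it cannot be relied on as a confirmation rule.

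**Conclusion.** No change is needed. Counting laboratory evidence in disease status is a fair trade-off between benign elevations and ambiguous imaging, and 3.3.3 and 5.2 apply it consistently. The undefined DFS event is missing detail that an analyst can fill from those sections: death, or the first recorded evidence of recurrence in a patient who had reached CR. A marker-only rise fits that reading, because 3.3.3 already labels it evidence of recurrence.

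The likely cost is modest. Power for a CR comparison that the plan does not power falls by at most 1.4 points if r is 2.5% or less, and by 6.4 points (91.8% to 85.4%) at the 10% upper end. This rests on assumed testing and benign-elevation rates, on borrowed CR rates, and on benign rises being unrelated to DNA-marker status. If they were related, the association could be distorted rather than merely diluted; the documents give no basis for sizing that. The key overall-survival analysis and its 89% power do not depend on any of this.
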